8.2 Pregnancy

Pregnancy in and of itself, is not regarded as an AE. A confirmed pregnancy in a participant (by urine or blood test) should be reported to the DCC via the Advantage eClinical system as soon as the Investigator has been made aware of the pregnancy. The decision to terminate the participant from the study will be made by the PI or designee and the participant following consultation with the DSMC. The PI or designee will use his/her expert judgment, based on an assessment of the potential benefit/risk to the participant, to determine if it is in the participant's best interest to continue participation in the study.

The pregnancy should be followed until an outcome is known. The outcome of all such pregnancies (i.e., spontaneous miscarriage, elective termination, still births, normal birth or congenital abnormality) must be documented and followed-up on a case report form that will be provided by the DCC. The pregnancy will be followed until an outcome, including any premature termination, must be reported to the DCC. All live births must be followed for a minimum of 30 days or to the first well-baby visit. All reports of congenital abnormalities/birth defects and spontaneous abortions/miscarriages should be reported as an SAE for this study. Elective abortion procedures, without complications, should not be considered as AEs unless they require hospitalization.

8.3 Vision Threatening Adverse Events

An adverse event will be considered vision-threatening and reported as an SAE if it has one of the following features:

- A vision loss of > 30 letters on the ETDRS chart compared to the last measurement provided the vision loss lasts > 1 hour.
- Resulting BCVA is light perception or worse for > 1 hour.
- Surgical intervention (including ocular procedures such as laser or cryopexy, intraocular injections, or aspiration of fluid) is required to prevent permanent loss of vision.
- There is severe intraocular inflammation (4+ cell in the anterior chamber or vitreous).
- Medical intervention is required to prevent permanent vision loss in the opinion of the investigator.

8.4 Causality

The Investigator will use the following question when assessing causality of any adverse event to study treatment: Is there a reasonable possibility that the administered cellular product caused the event? An affirmative answer designates the event as a suspected adverse reaction.

In addition, each adverse event will be assessed for its relationship to study procedures, including the injection itself. The Investigator will use the following question when assessing causality of an adverse event to study procedure: Is there a reasonable possibility that the intravitreal injection procedure caused the event?

The Medical Monitor at the DCC is available for consultation on assessing causality. For SAEs, the Medical Monitor will evaluate all reported SAEs against all accumulating knowledge regarding the study treatment. If the Medical Monitor's causality determination differs from the Investigator's assessment, the Medical Monitor's determination will prevail for regulatory reporting purposes.

8.5 Naming and Grading of Adverse Events

Each adverse event will be graded for severity based on the severity grading outlined below:

- Grade 1 (Mild) An AE that is easily tolerated by the participant, causing minimal discomfort and not interfering with everyday activities.
- Grade 2 (Moderate) An AE that is sufficiently discomforting to interfere with normal everyday activities.
- Grade 3 (Severe) An AE that prevents normal, everyday activities. In adults, such an AE would, for example, prevent attendance at work/school and would necessitate the administration of corrective therapy.

All adverse events will be followed by the Investigator until resolution or up to one month after study termination or until the study participant is lost to follow-up. The Investigator will treat or observe participants with adverse events as appropriate for standard of care and follow the participants at regular intervals until resolution or stabilization of the adverse event.

8.6 Adverse Event Reporting

Each adverse event will be recorded in the participant's medical record and the adverse event source document will be completed by the Study Coordinator and Investigator. The Study Coordinator completing the adverse event documentation form will be the study coordinator assigned to the visit and may be masked or unmasked depending on the visit. The information will be transmitted to the DCC using Advantage eClinical. All serious adverse events will be reported to the DCC within 24 hours of its occurrence and/or the site's knowledge of the event. All other adverse events will be reported to the DCC within 7 days of the site becoming aware of the event.

APPENDIX B: Determining Childbearing Potential

A female participant who is considered non-childbearing due to a medical condition (i.e., participant has previously undergone a hysterectomy) does not need a pregnancy test, Follicle-stimulating Hormone (FSH) test, or contraception.

If a female participant is considered non-childbearing due to menopause, it must be in accordance with the following guidance on the definition of menopause. This guidance defines menopause as:

Women over age 55 who have not had a period for one year will be considered menopausal and do not need a pregnancy test, FSH test, or contraception.

Women between 50 and 55 who have not had a period for one year should have an FSH test. If their FSH level is \geq 20 mIU/mL, they will be considered menopausal and do not need pregnancy testing or contraception. If their FSH level is < 20 mIU/mL, they will need pregnancy testing and contraception as required by the protocol.

Women between 45 and 50 who have not had a period for one year will need both an FSH test and a pregnancy test. If they are not pregnant and their FSH level is \geq 20 mIU/mL, they will be considered menopausal and will not require contraception or additional pregnancy testing. If their FSH test is < 20 mIU/mL, they will need pregnancy testing and contraception as required by the protocol.

1.0 STUDY SYNOPSIS

The goal of this phase I/II prospective, randomized, sham-controlled, double-masked clinical trial is to determine whether intravitreal autologous CD34+ stem cell therapy is safe, feasible and potentially beneficial in eyes with vision loss from central retinal vein occlusion (CRVO). Retinal Vein Occlusion (RVO) is a leading retinal vascular cause of vision loss in the elderly. CD34+ stem cells in human bone marrow are mobilized into the circulation in response to tissue ischemia for tissue revascularization and repair. Since local delivery of CD34+ stem cells benefits ischemic tissue, intravitreal delivery of CD34+ stem cells may benefit vision and retinal ischemia in eyes with RVO. A pilot clinical trial has shown no major safety or feasibility concerns using intravitreal autologous CD34+ bone marrow stem cells. In this proposed expanded phase I/II study, approximately 20 participants (20 eyes) with persistent vision loss from CRVO will be enrolled and followed for 1 year. Only eyes with CRVO will be enrolled to maintain uniformity in the study population. Total study duration will be approximately 60 months. This single-center study will be conducted at the University of California Davis (Enrollment Center). The Data Coordinating Center will be Emmes. The Study Chair/Principal Investigator will be [name]. The study will be conducted under an IND cleared from the FDA. A Data and Safety Monitoring Committee (DSMC) will oversee the study. Participants will be randomized 1:1 to immediate cell therapy/deferred sham therapy or immediate sham therapy/deferred cell therapy, where deferred therapy refers to the therapy administered at month 6 and immediate therapy refers to therapy administered at baseline (either sham or cellular). At month 6, the (immediate) cell treated eye will receive sham treatment and the (immediate) sham treated eye will receive cellular therapy. The cell therapy involves a bone marrow aspiration, isolation of CD34+ cells from the aspirate under Good Manufacturing Practice (GMP) conditions, and intravitreal injection of the isolated CD34+ cells. The sham therapy involves a sham bone marrow aspiration with penetration of the skin but with no penetration of the bone and a sham injection without penetrating the eye. The participant, examining ophthalmologist, visual acuity examiner, photographers and OCT, perimetry, and ERG technicians will remain masked to study treatment assignment for study duration. A comprehensive eye examination with ETDRS best-corrected visual acuity, optical coherence tomography (OCT) and OCT angiography (OCTA), autofluorescence, fundus photography, fluorescein angiography, microperimetry, and electroretinography will be performed at baseline and serially. A subset of participants with good fixation on microperimetry and clear media on exam and commercial-grade OCTA and who give consent will have ultra-high resolution cellular retinal imaging using research-grade OCT and OCTA and adaptive optics-OCT at baseline. These participants with high quality images at baseline will have repeat imaging at 1 month after receipt of cellular treatment, with at least 2 of the participants randomized to the immediate sham therapy/deferred cellular therapy arm also having imaging 1 month after sham therapy. Postrelease flow cytometry characterization will be performed to determine the composition of the CD34+ enriched final product in terms of hematopoietic versus angiogenic stem cells based on cell surface markers (i.e., CD133(+)/CD45(+)/CD34(+) vs CD31(+)/VEGFR-2(+)/CD45(-) /CD34(+)) provided there are an adequate number of cells, as determined by the GMP lab. The primary outcome measures for the safety and feasibility of the stem cell therapy will be the incidence and severity of ocular and systemic adverse events reported during Study Period 1 (i.e., the day of the first treatment (Treatment 1) up to but not including the day of the second treatment (Treatment 2)) and the mean and range of number of CD34+ cells isolated and the number injected into the eye. The secondary safety outcome measures are the incidence and severity of ocular and systemic adverse events reported throughout study duration. The secondary efficacy outcome measures will be the changes in visual function, retinal perfusion and morphology following cell therapy. The long-term objective is to determine whether intravitreal autologous CD34+ cell therapy can minimize, or reverse vision loss associated with retinal ischemia without compromising safety.

2.0 STUDY OBJECTIVES

2.1 Primary Objective

The primary objective of the study is to assess the safety and feasibility of the stem cell therapy, which will be evaluated using the following primary outcome measures:

- Primary safety outcome: Incidence and severity of ocular and systemic adverse events reported during Treatment Period 1 (i.e., the day of the first treatment (Treatment 1) up to but not including the day of the second treatment (Treatment 2)).
- Feasibility outcome: The mean and range of number of CD34+ cells isolated from the bone marrow aspirate and number injected into the eye.
- Secondary safety outcome: Incidence and severity of ocular and systemic adverse events reported throughout study duration.

2.2 Secondary Objective

The secondary objective is to explore the effect of stem cell therapy on retinal function and morphology. Secondary efficacy outcomes include changes in best corrected visual acuity (BCVA), microperimetry, OCT/OCTA, electroretinography (ERG), fundus photography, fluorescein angiogram, autofluorescence and quality of life.

2.3 Exploratory Objective

Exploratory aims include descriptive analysis of changes in the retina and retinal vasculature at a cellular level using adaptive optics-OCT imaging, descriptive and quantitative analysis of changes in retinal vascular density and retinal morphology using ultrahigh resolution swept-source OCT and OCTA. An additional exploratory aim includes quantitative analysis of the hematopoietic and endothelial stem cell subcomponents and subcomponent of cells with VEGFR-2 in the harvested CD34+ population. A study survey will collect participants' experiences with various aspects of the study, including their impressions on when they received stem cell injection vs sham injection.

3.0 STUDY DESIGN

3.1 General Design and Plan

This is a phase I/II randomized, prospective, double-masked, sham-controlled study to determine the feasibility, safety and potential efficacy of intravitreal injection of autologous adult CD34+ stem cells from bone marrow (herein referred to as cellular therapy) in participants with vision loss from CRVO.

All potential participants diagnosed with CRVO will be screened by the PI or designee for study eligibility based on available clinical information. Those whose medical record suggests they may be eligible for the study will be asked to attend one or more screening visits at the UC Davis Eye Center. Informed consent will be obtained prior to conduct of any study procedures. Participants will undergo pre-treatment screening assessment and baseline testing to evaluate the extent of the condition and to confirm eligibility for the study. Once the participant is confirmed to be eligible, he/she will be randomized 1:1 to immediate cell therapy/deferred sham therapy or immediate sham therapy/deferred cell therapy.

Participants who are randomized to immediate cell therapy/deferred sham therapy will undergo a bone marrow aspiration followed by intravitreal injection of isolated CD34+ cells after baseline testing. Follow-up assessments will occur at 1 day, 1 week, 1 month, 3 months and 6 months post stem cell injection. Within 1 month of the 6-month follow-up study visit, participants will receive a sham bone marrow aspiration and sham injection. At least 1 day will separate the 6-month follow-

up study visit and the sham therapy. Participants will continue to be followed at 1 day, 1 week, 1 month, 3 months, and 6 months for a total follow-up of 12 months after the stem cell injection (and 6 months following the sham injection). For participants who did not complete the study satisfaction survey at the 12-month visit, an exit visit may occur following the 12-month visit to allow the survey to be completed.

Participants who are randomized to immediate sham therapy/deferred cell therapy will undergo a sham bone marrow aspiration followed by sham injection after baseline testing. Follow-up assessments will occur at 1 day, 1 week, 1 month, 3 months and 6 months post sham injection. Within 1 month of the 6-month follow-up study visit, participants will undergo a bone marrow aspiration followed by intravitreal injection of isolated CD34+ cells. At least 1 day will separate the 6-month follow-up study visit and the cellular therapy. Follow-up assessments will occur at 1 day, 1 week, 1 month, 3 months, and 6 months thereafter for a total follow-up of 12 months after the sham injection (and 6 months following the stem cell injection). For participants who did not complete the study satisfaction survey at the 12-month visit, an exit visit may occur following the 12-month visit to allow the survey to be completed. The study schema is provided in Section 2.0 of the protocol and Table 2 of the protocol details the schedule of evaluations.

3.2 Sample Size Considerations

There is no formal sample size calculation for this small phase I/II study and no formal hypothesis testing will be performed. A sample size of 20 participants was chosen to ensure that it is financially feasible to conduct the study and logistically possible to complete the study enrollment within the study period. The primary objective is to assess the safety and feasibility of the stem cell therapy; however, it is desired to obtain some gauge of potential efficacy of this cell therapy. Thus, participants will be randomized 1:1 to immediate cellular therapy/deferred sham or immediate sham/deferred cellular therapy. After their first treatment (cellular or sham), participants will be followed for 6 months, at which time participants who initially received sham treatment will be given stem cell treatment and vice versa. The small sample size is not ideal, but for practical purposes, it would be difficult to increase the sample size significantly without increasing the enrollment period for the study.

Although the study as designed may not be large enough to determine efficacy, some efficacy signals might be observed with the current study design. Such a signal may warrant further investigation of this therapy for CRVO. When a phase II/III randomized controlled trial is planned, appropriate sample size calculations will be performed.

It is recognized that the study has limited power to show efficacy; however, we hope to obtain some trends in change in visual function or retinal morphology or perfusion that may suggest efficacy to justify a larger randomized prospective clinical trial. Power calculations are explored in section 5.2.2 for the proposed method of analyzing the secondary outcomes.

3.3 Randomization

Randomization will occur after informed consent has been obtained and once a participant is confirmed to be eligible. Randomization will need to occur prior to the baseline visit for logistical and scheduling reasons. Much coordination among the hematologist, the Good Manufacturing Practices (GMP) facility, and the treating ophthalmologist needs to occur on days in which the cellular therapy is given. Therefore, knowing which treatment arm to which the participant has been randomized prior to the baseline visit is necessary. Great care will be taken to choose participants who are highly motivated to participate so as to prevent drop-out post-randomization.

A secure, internet-based eligibility, enrollment, and randomization system is integrated into the study to control and document the randomization assignments. Eligible participants will be randomized in a 1:1 ratio to immediate cellular therapy/deferred sham therapy or immediate

sham/deferred cellular therapy. Random assignments are generated and maintained by the Data Coordinating Center (DCC).

3.4 Masking

3.4.1 Type of Masking

This is a double-masked, sham-controlled trial, in which participants, visual acuity examiners, examining ophthalmologists, study photographers and technicians will remain masked to treatment assignment during study duration.

3.4.2 Maintenance of the Masking

To maintain the masking for the study duration of each participant's follow-up period, there will be separate ophthalmologists designated for administration of study therapy and study visit follow-up examination after study therapy (**TABLE 1**). The PI will remain masked as the examining ophthalmologist for the study duration. The treating ophthalmologist will be an experienced retinal specialist and faculty member of the UC Davis Eye Center. He/she will remain unmasked to therapy assignment and perform the eye examinations during the first week of each participant's follow-up after sham or cell therapy. An experienced retinal specialist from the Enrollment Center will be available as a backup unmasked treating ophthalmologist, and a separate experienced retinal specialist from the Enrollment Center will be available as a masked examining ophthalmologist. However, all efforts will be made to have the study therapy administered by the main treating ophthalmologist and all masked study examinations performed by the masked examining ophthalmologist (PI) to minimize confounding variables.

Study Coordinators from the UC Davis Eye Center Clinical Trials Team will be assigned to the study to manage the day-to-day activities regarding the study under the supervision of the PI, with the unmasked Study Coordinator being provided only general guidance from the PI. The unmasked Study Coordinator will coordinate and schedule all unmasked study visits and therapies.

The masked and unmasked Study Coordinators will be responsible for scheduling all study visits taking utmost care to preserve the masking. Prior to randomizing the participant, the masked Coordinator will schedule the Treatment 1 and Treatment 2 study visits working under the pretense that both procedures involve stem cell therapy. Once the participant is randomized, the unmasked Study Coordinator will provide both the study hematologist and the GMP laboratory with information regarding which Treatment study visit will require bone marrow/cellular therapy and which will require sham aspiration/sham injection. The unmasked Study Coordinator will also schedule the post Treatment Day 1 and Week 1 study visits for both Study Periods.

The visual acuity examiners and photographers and technicians obtaining fundus photographs, fluorescein angiograms, OCT/OCTA and autofluorescence imaging, microperimetry and electroretinography (ERG) will be masked to study treatment assignment to avoid bias in outcome assessment. The advanced retinal imaging team, however, will be unmasked for the duration of the study.

Table 1: Masking of Treatment Assignment of EnrollmentCenter Personnel			
	Masked Status		
Principal Investigator	Masked		
Examining Ophthalmologist	Masked		
Masked Study Coordinator	Masked		
Hematologist	Unmasked		
Visual Acuity Examiner	Masked		
Treating Ophthalmologist	Unmasked		
Unmasked Study Coordinator	Unmasked		
Photographers	Masked		
OCT Technicians	Masked		
Perimetry Technicians	Masked		
ERG Technicians	Masked		
Study Participants	Masked		
Advanced Retinal Imaging Team	Unmasked		
GMP Laboratory Team	Unmasked		

All DCC staff will be unmasked to treatment assignment throughout a participant's follow-up. Knowledge of the treatment assignment by DCC staff will not affect assessment of therapy outcome as there will be little to no interaction of DCC staff with visual acuity examiners, examining ophthalmologists, study photographers or technicians, or study participants. Care will be taken when DCC staff are conversing with site personnel. DCC staff will be trained in the masked status of each site staff member especially the Study Coordinators to ensure that during regular communications information that may be unmasking is not inadvertently provided. The electronic data capture system will be designed in such a way that masked staff will not have access to any data related to therapy or adverse events reported during the first month following therapy as this information is potentially unmasking.

While the study is ongoing, site personnel, including the Study PI, will not have access to cumulative summaries of study findings broken down by treatment arm. Instead, these summaries will be presented only to the DSMC within a closed session in which only the DSMC members and select DCC staff (e.g., study statistician) are present. Although not fail-safe, restricting access in this way will help prevent unintentional changes in study implementation.

3.5 Unmasking

There are no anticipated circumstances in which it may be necessary to unmask a particular study participant before completion of follow-up. However, in the rare case that it becomes necessary, the request to unmask an individual participant will be made by the Study PI. Unmasking the participant should be made only in cases of medical emergency when knowledge of the treatment group assignment may be necessary for clinical management and decision making. The decision to unmask a participant will be made by the Study Principal Investigator and the DCC Medical Monitor.

3.6 Participant Discontinuation / Replacement

In the event that a participant is terminated from the study after randomization and prior to receipt of treatment (cellular or sham) at the Treatment 1 visit regardless of the reason, an additional participant will be accrued as a replacement. In the event that a participant receives the first treatment but opts not to receive the second treatment, an additional participant will be accrued as a replacement, but the original participant will be encouraged to return for all study visits to ensure the participant's safety is not compromised. The replacement participant will receive both treatments and will be followed for 12 months, the same as any other participant enrolled in the study. If a participant is terminated or withdraws from the study following the receipt of the second treatment, the participant will again be encouraged to return for all study visits for safety monitoring but will not be replaced. A maximum of one participant may be replaced, regardless of timing of withdrawal.

Table 2 contains these follow-up and replacement decisions for each scenario.

Scenario		Original Participant Follow-up	Included in ITT?	Replacement Decision		
1	Participant terminates/withdraws after randomization prior to cellular/sham therapy on Day 0 (includes inadequate sample following bone marrow aspiration)	No further assessments performed; participant only followed to close-out any AEs.	No	Additional patient will be accrued as a replacement		
2	Participant receives 1 st treatment but withdraws during Period 1 / refuses further treatment	Participant encouraged to follow visit schedule at least through Month 6 or longer (for safety monitoring)	Yes	Additional participant will be accrued as a replacement (up to 1 time)		
3	Participant has inadequate sample following bone marrow aspiration (period 2)	Participant cannot receive 2 nd treatment; is necessarily unmasked	Yes	Additional participant will be accrued as a replacement (up to 1 time)		
4	Participant receives 2 nd treatment but withdraws during Period 2	Participant encouraged to follow visit schedule through Month 12 (for safety monitoring)	Yes	No replacement		

Table 2: Participant Follow-up and Replacement Decisions

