4.1.2 Intent-to-Treat Population

The (modified) intent-to-treat population consists of all participants who were randomized and received the first injection (cellular or sham). For analyses, these participants will be analyzed in the arm to which they were randomized.

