4.3 Tables, Figures and Listings Conventions

Safety analyses will be summarized for the safety population. All other analyses described in this document will be done for the ITT population and summarized by randomized treatment group and overall. For all summaries of ITT population, participants will be analyzed according to the treatment arm to which they were randomized regardless of the subsequent sequence of events regarding study drug exposure.

Continuous variables will be summarized using the following descriptive statistics: n (non-missing sample size), mean, standard deviation, percentiles (median, maximum, and minimum). Categorical variables will be summarized in terms of frequencies and/or percentages.

Any deviations from the above general conventions will be noted in the subsequent sub-sections.

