7.1.2 Feasibility

The number and percent of study participants undergoing successful bone marrow aspiration will be summarized. The mean and range of volume of bone marrow aspirate, number of CD34+ cells isolated and number of CD34+ cells injected intravitreally will be described to determine whether a desired number of stem cells can be isolated from bone marrow aspiration without sedation in an outpatient setting. Any participant who did not tolerate the bone marrow aspiration without sedation without sedation and any unsuccessful bone marrow aspiration attempt will be recorded.

Other pre- and post-release analysis parameters such as percent yield of the CD34+ isolation will also be described.

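### Feasibility is analysed on the modified ITT population, so an inadequate Treatment 1 harvest drops out of the summary of CD34+ cells isolated, while the same failure in Period 2 stays in

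*SAP*

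**What the plan says.** The feasibility outcome in SAP 2.1 is "The mean and range of number of CD34+ cells isolated from the bone marrow aspirate and number injected into the eye". SAP 7.1.2 gives its purpose: "to determine whether a desired number of stem cells can be isolated from bone marrow aspiration without sedation in an outpatient setting".

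Four places fix who is counted:

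- **SAP 3.6, Table 2.** Scenario 1 covers a participant who leaves "prior to cellular/sham therapy on Day 0 (includes inadequate sample following bone marrow aspiration"; the ITT column says No and a replacement is accrued. Scenario 3 reads "Participant has inadequate sample following bone marrow aspiration (period 2"; the ITT column says Yes.
- **SAP 4.1.2.** The modified ITT population "consists of all participants who were randomized and received the first injection (cellular or sham".
- **SAP 4.3.** "Safety analyses will be summarized for the safety population. All other analyses described in this document will be done for the ITT population". It adds: "Any deviations from the above general conventions will be noted in the subsequent sub-sections".
- **SAP 11.0.** Both feasibility outputs and the clotting table carry the label ITT.

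Section 7.1.2 notes no deviation from 4.3. It does say that "any unsuccessful bone marrow aspiration attempt will be recorded".

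The protocol is looser. Its modified ITT rule appears only under Efficacy (7.8.2.2), and its feasibility text (7.8.2.1) speaks of study participants without that restriction.

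**The concern.** Feasibility asks whether enough cells can be obtained. A harvest that yields too few is the most informative negative result on that question. An analysis set that requires the first injection removes exactly those results at Treatment 1.

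Only the immediate-cell arm can lose them, because a sham aspiration produces no sample that could fail. The pre- and post-release summary is laid out by treatment arm, so yields filtered on success in one arm would stand beside unfiltered yields in the other. The clotting table (SAP 7.1.3), which sets clotting beside each participant's cell number, would lose the same harvests.

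**Working it through.** **Step 1. Trace one failed harvest.**

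| | Failure at Treatment 1 | Failure in Period 2 |
|---|---|---|
| First injection received? | No | Yes (sham) |
| In ITT (Table 2, 4.1.2)? | No | Yes |
| In feasibility summaries (4.3, 7.1.2)? | No | Yes |
| Yield in mean and range isolated? | No | Yes |
| In-study value for number injected? | None | None |

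The last row shows that only the isolated component is affected.

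**Step 2. Put the inputs on the isolated scale.** The plan states no expected yield or failure rate, so there is no figure to reproduce. Protocol 6.1.5 resuspends the cells in 0.15 cc and sends 0.1 cc, with at least 800,000 viable cells, for injection. Protocol 7.3 anticipates about one million injected on average. Both figures are on the injected scale. Assuming a uniform suspension, multiply by 0.15/0.10 = 1.5:

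- minimum: 0.8 × 1.5 = 1.2 million isolated
- average: 1.0 × 1.5 = 1.5 million isolated

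**Step 3. Effect on the mean.** Let n successful harvests average 1.5 million and one failed harvest yield Y. The mean over all aspirates is (1.5n + Y)/(n + 1); the plan reports 1.5. Take Y from 0 to 1.19 million, just under 1.2.

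| Set | Y = 0 | Y = 1.19 |
|---|---|---|
| Overall, n = 20 | 30.00/21 = 1.429; overstated 5.0% | 31.19/21 = 1.485; overstated 1.0% |
| Immediate-cell arm, n = 10 | 15.00/11 = 1.364; overstated 10.0% | 16.19/11 = 1.472; overstated 1.9% |

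The overall row assumes that the failure is replaced (at most one replacement is allowed) and that the other 20 harvests succeed. The arm row also assumes that the replacement joins the same arm, which the documents do not state.

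**Step 4. Effect on the range.** The true minimum would be Y if the failure is the lowest yield, and Y is then not reported. The release minimum is on viable cells, so a harvest that fails on viability could have an ordinary isolated count. Loss of the low end is likely, not certain.

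**Step 5. Effect on the success percentage.** SAP 7.1.2 does not define a successful aspiration.

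- If it means adequate product: 20/21 = 95.2% (exact 95% interval 76.2 to 99.9) is reported as 20/20.
- If it means marrow obtained: 21/21 is reported as 20/20, both 100%, with no bias.

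**Step 6. How likely is a failure?** For an assumed per-harvest failure rate p and 10 first harvests, the chance of at least one is 1 − (1 − p)^10.

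| p | 1% | 2% | 5% | 10% | 20% |
|---|---|---|---|---|---|
| Chance | 9.6% | 18.3% | 40.1% | 65.1% | 89.3% |

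Protocol 4.0 reports that the pilot obtained a desired number in each participant. It describes six published and nine enrolled participants, and which group the statement covers is unclear. Zero failures gives a one-sided 95% upper limit of 1 − 0.05^(1/6) = 39.3% for six, or 1 − 0.05^(1/9) = 28.3% for nine.

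**The case against.** **Failures are recorded.** The sentence in 7.1.2 on unsuccessful attempts has no population limit, and the CONSORT diagram (labelled Prescreened) may count these participants. This stands in part: the data should exist, and a reader who infers that failures would be invisible goes too far. But recording an attempt does not put its yield in the mean, the range or a denominator. The table shells, which might settle the layout, are not in the documents.

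**The Section 11 labels are unreliable.** They mark safety outputs ITT, against 4.3, and repeat some titles. This is fair, so the labels are only supporting evidence. The rule in 4.3, with no exception in 7.1.2, gives the same result without them.

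**Treating the two periods differently is normal.** This is correct. A Period 2 failure belongs in a modified ITT set because the first injection was given. The asymmetry is not itself an error; the error is using that set for feasibility.

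**The effect is small and conditional.** This is also fair. The mean moves little, the outcome is descriptive, and no between-arm test of yield is planned.

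Two stronger readings are tempting. One is that the whole feasibility outcome is biased; the number injected is not, because a failed harvest has no in-study injection in either period. The other is that the reported minimum of cells isolated cannot fall below 800,000; that figure applies to the viable cells in the injected volume, not to the total isolated.

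**Conclusion.** The point holds for cells isolated, for the clotting table and, under one reading of success, for the success percentage. It is a stated population rule that biases these summaries in the favourable direction whenever a low-yield Treatment 1 harvest is excluded; it is not merely missing detail. The SAP introduces it, since the protocol does not restrict feasibility in this way.

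The bias in the mean is modest: 1.0% to 5.0% overall for one failure, and 1.9% to 10.0% in the immediate-cell arm under the replacement assumption. The low end of the range and the success percentage matter more, because they bear most directly on whether enough cells can be obtained. All sizes rest on a uniform suspension, a 1.5 million average isolated and an undocumented failure rate. The documents do not show that any Treatment 1 harvest has failed or will fail.

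The Section 11 safety labels, the pre-treatment AE listing missing from Section 11 and the timing rule in SAP 4.2.5 are separate minor reconciliations and do not support this conclusion. The point should be fixed because a primary outcome is involved and the correction is cheap.

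**What to change.** In SAP 7.1.2 and in the Section 11 feasibility and Clotting Data rows, define a feasibility population: all participants in whom a real bone marrow aspiration was started, in either period, whether or not cells were injected. Then:

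- include every aspirate's yield in the mean and range of cells isolated;
- define a successful harvest against the minimum already in the protocol, and report it overall and by period;
- report the number injected among those injected, and say so.

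The modified ITT set can stay as it is for efficacy.

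The cost is SAP wording and table labels. Protocol 7.6 already depends on a count below the minimum being known, and 7.1.2 has unsuccessful attempts recorded, so no new data collection appears necessary, although the forms are not in the documents. The only downside is that reported feasibility may be slightly less favourable.
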